### **7.6.8.1 Incidence of IMAE**

IMAEs will be summarized for each category:

- Overall summary of any IMAEs by worst CTC grade presented by Category/PT (any grade, grade 3-4, grade 5)
- Overall summary of any serious IMAEs by worst CTC grade presented by Category /PT (any grade, grade 3-4, grade 5)
- Overall summary of any IMAEs leading to discontinuation by worst CTC grade presented by Category/PT (any grade, grade 3-4, grade 5)
- Overall summary of any IMAEs leading to drug delay by worst CTC grade presented by Category/PT (any grade, grade 3-4, grade 5)
- Overall summary of drug-related IMAEs by worst CTC grade presented by Category/PT (any grade, grade 3-4, grade 5)
- Overall summary of drug-related IMAEs leading to discontinuation by worst CTC grade presented by Category/PT (any grade, grade 3-4, grade 5)
- Overall summary of any IMAEs by worst CTC grade presented by Category/PT (grade 1, 2, 3, 4, 5, unknown)
- Overall summary of any serious IMAEs by worst CTC grade presented by Category/PT (grade 1, 2, 3, 4, 5, unknown)
- Overall summary of any IMAEs leading to discontinuation by worst CTC grade presented by Category/PT (grade 1, 2, 3, 4, 5, unknown)
- Overall summary of any IMAEs leading to drug delay by worst CTC grade presented by Category/PT (grade 1, 2, 3, 4, 5, unknown)

The analyses will be conducted using the 100-day safety window.

By-subject IMAE listing will be provided.

### **7.6.8.2 Time-to onset of IMAE**

Time-to onset of the following specific events will be summarized for each category of IMAEs:

- Time-to onset of any grade IMAE
- Time-to onset of grade 3 to 5 IMAE
- Time-to onset of any grade IMAE where immune modulating medication was initiated
- Time-to onset of grade 3 to 5 IMAE where immune modulating medication was initiated

The following summary statistics will be reported for treated subjects who experienced at least one immune-mediated adverse event from the category: median, min and max. Median time to onset along with 95% confidence interval using the Kaplan-Meier technique is also reported for all treated subjects. If the subject did not experience a IMAE in the category, time-to onset will be censored at the maximum follow-up time of all subjects in their respective treatment group (i.e. for subjects without an event, follow-up time is defined from first dosing date up to last dosing date +100 days if subjects are off treatment and followed for at least 100 days, otherwise it is defined up to the last known alive date).

See time-to onset definition subsection of [Appendix 1](#) for additional details. The analyses will be conducted using the 100-day safety window.

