## **8 STATISTICAL CONSIDERATIONS**

### **8.1 Sample Size Determination**

In general, for nivolumab monotherapy, the safety profile to date is similar across tumor types, while IMAEs of high grade (Grade 3-4) are rather uncommon. Their overall incidence was 6% in a previous Phase 1 trial that tested nivolumab at doses between 0.1 mg/kg to 10 mg/kg in 306 subjects with different recurrent or refractory malignancies (MDX-03).

In order to further characterize the frequency and outcome of such apparently infrequent safety events, the current study will treat approximately 150 subjects with nivolumab. This sample size will allow for estimating an incidence rate of 0.67% (n=1 subject with events) with a 95% CI (confidence interval) of (0.02%, 3.7%), or an incidence rate of 2% (n=3 subjects with events) with a 95% CI of (0.4%, 5.7%). Furthermore, the sample size will allow for enough events to compare incidence in large community practice with historical adverse event data.

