**Table 8.1-1: Estimated Incidence Rates and 95% CIs**

Sample Size	Incidence Rate (%)	Lower 95% CI (%)	Upper 95% CI (%)
150	0.67	0.02	3.66
150	1.0	0.16	4.73
150	2.0	0.41	5.73
150	5.0	2.33	10.24
150	10.0	5.71	15.96
150	11.0	6.74	17.52
150	12.0	7.27	18.30
150	13.0	8.34	19.84
150	14.0	8.88	20.60
150	15.0	9.98	22.11
150	16.0	10.53	22.86
150	17.0	11.65	24.36
150	18.0	12.21	25.10
150	19.0	13.35	26.57
150	20.0	13.92	27.30
150	21.0	15.07	28.76
150	22.0	15.65	29.49
150	23.0	16.82	30.93
150	24.0	17.41	31.65
150	25.0	18.59	33.07

The number of subjects who are evaluable for AEs in the study will be 150. We make the conservative assumption based on Motzer that the rate of IMAEs of grades 3-5 is 13%. The primary goal of the present study is to address whether the rate is consistent with the rate reported in the Motzer study in the sense that the final 95% confidence interval is wholly less than 20%. As indicated in Table 8.1-1, this would happen if the observed rate is less than 13.3% or less (20/150 or fewer grade 3-5 IMAEs). The trial has 61% power to demonstrate consistency of rates in the sense that the probability is 61% of showing the upper bound of the 95% confidence interval is less than 20% when the true rate is 13%. The trial has 80% power to demonstrate the consistency of rates when the true rate is 11.5%

The observed rate may be somewhat larger than 13.3% and will still be consistent with expectations regarding safety, although it may raise concerns that the present population may be different from that of the Motzer study or that the assessment of AEs is different in the two studies. Only if the 95% confidence interval extends beyond 25% would the results of the study raise

serious safety concerns. This would happen if the observed rate is at least 18% (27/150 or more grade 3-5 STRAEs), see [Table 8.1-1](#). Again assuming that the true rate is 13%, the power of the study, the probability that the 95% confidence interval is wholly less than 25% (and so the observed rate is less or equal to 18%) is 95%. Also, if the true rate in the present study is actually 15%, the probability of showing that the 95% confidence interval is wholly less than 25% is 82%.

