### 8.3.2 Secondary Endpoint(s)

The secondary objective of the study will be assessed by measuring the following:

- median time to onset, median time to resolution of high grade (Grade 3-4) IMAEs
- percentage of subjects who received immune modulating medication (e.g. corticosteroids, infliximab, cyclophosphamide, IVIG, and mycophenolate mofetil), or hormonal replacement therapy, the percentage of subjects who received  $\geq 40$  mg prednisone equivalents, total duration of all immune modulating medications given for the IMAE and summary of subjects with resolution of AES after initiating these therapies.

[REDACTED]

- [REDACTED]
- █ [REDACTED]
- █ [REDACTED]
- █ [REDACTED]
- █ [REDACTED]
- █ [REDACTED]

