### **7.6.2 Secondary Analyses**

Additional descriptive statistics will include median values using the Kaplan-Meier (KM) product-limit method with 95% CI using Brookmeyer and Crowley of time to onset and time to resolution of IMAEs, and will be presented for all treated subjects in Groups 1, 2, and 3. Time to onset is calculated from first dosing date to the event onset date. If a subject never experienced the given AE, the subject will be censored at the last contact date. Time to resolution is calculated from the AE onset date to AE end date. If an AE is ongoing at the time of analysis, the time to resolution will be censored at the last contact date.

Management of high-grade (CTCAE v4.0 Grade 3-4 and Grade 5) IMAEs will be characterized by measuring percentage of subjects who received immune modulating medication (or hormonal replacement therapy), percentage of subjects who received  $\geq 40$  mg prednisone equivalents, and total duration of all immune modulating medications given for the event, in all treated subjects who have experience high-grade (CTCAE v4.0 Grade 3-4 and Grade 5) IMAEs and all subjects in Groups 1, 2, and 3.

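### At the assumed 13% rate, the all-treated Kaplan-Meier median time to onset of Grade 3-5 IMAEs will almost certainly not be reached, leaving no onset estimate with a usable confidence interval

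*SAP*

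**What the plan says.** Protocol 8.3.2 lists as a secondary endpoint "median time to onset, median time to resolution of high grade (Grade 3-4) IMAEs". SAP 4.2 lists the same endpoint with Grade 5 added. Neither names an estimator or a population.

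The analysis text does. SAP 7.6.2 plans "median values using the Kaplan-Meier (KM) product-limit method with 95% CI using Brookmeyer and Crowley of time to onset", presented for treated subjects in Groups 1, 2 and 3. Subjects who never have the event are censored at last contact. The Analyses part of the protocol synopsis says the same for high-grade IMAEs. Protocol 8.4.3 (Secondary Analyses) is in the table of contents, but its text is not in the copy reviewed, so nothing here rests on it.

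SAP 7.6.8.2 works by IMAE category, for any grade and for Grade 3 to 5, and gives two summaries. The first is a median, minimum and maximum among subjects who had an event in the category. The second is: "Median time to onset along with 95% confidence interval using the Kaplan-Meier technique is also reported for all treated subjects". Event-free subjects are censored at the largest follow-up time in their group. A parenthesis then describes follow-up subject by subject, to last dose + 100 days or last known alive date. Appendix 1 repeats this rule and says that the resulting plot shows the cumulative rate over time.

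On incidence, Protocol 8.1 assumes "that the rate of IMAEs of grades 3-5 is 13" per cent, all categories together. For Grade 3-4 events it also cites: "Their overall incidence was 6% in a previous Phase 1 trial". No any-grade or per-category rate is given.

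**The concern.** A Kaplan-Meier median is the time at which the estimated event-free proportion falls to one half. If every treated subject is in the analysis and only about one in eight is expected to have the event, the curve has no reason to fall that far. The output would then be not reached for the median and, in nearly all cases, for both confidence limits.

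At stake is the usefulness of a named secondary endpoint in a study whose purpose is safety. A reader wants to know when high-grade IMAEs occur and how precisely that is known. If the estimator assigned to the endpoint returns nothing, what remains is a by-category median and range with no measure of uncertainty, and SAP 7.6.2 does not say that this is the endpoint.

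**Working it through.** **Inputs from the documents.** From Protocol 8.1: "The number of subjects who are evaluable for AEs in the study will be 150"; a Grade 3-5 rate of 13%; the consistency rule "20/150 or fewer grade 3-5 IMAEs"; serious concern from 27/150. Group sizes of about 75, 50 and 25 are from Protocol 3.1. Treatment lasts at most 24 months, and IMAEs count up to 100 days after last dose.

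**The plan's own figures reproduce.** The exact (Clopper-Pearson) interval for 20/150 is 8.34% to 19.84%. P(X ≤ 20 | n = 150, p = 0.13) = 0.607 (stated 61%). P(X ≤ 20 | p = 0.115) = 0.800 (stated 80%). P(X ≤ 26 | p = 0.13) = 0.951 (stated 95%). P(X ≤ 26 | p = 0.15) = 0.821 (stated 82%). So 13% of 150 is the working scenario: 0.13 × 150 = 19.5 subjects affected.

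**Group-maximum censoring (SAP 7.6.8.2 as worded).** Nobody is censored before the last event, taking one common maximum, so the curve ends at S = 1 − x/n.

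- At x = 20: S = 1 − 20/150 = 0.867. With se(ln S) = √[20/(150 × 130)] = 0.0320, the log-log 95% limits are 0.80 and 0.91.
- At x = 27, the count at which Protocol 8.1 sees serious safety concern: S = 1 − 27/150 = 0.82, still far above 0.50.
- The median needs x ≥ n/2. P(X ≥ 75 | n = 150) is about 1e-27 at 13%, 4e-11 at 25% and 0.8% at 40%.
- A finite lower confidence limit needs the lower limit of S to fall to 0.50. That takes 63 events (log-log) or 64 (linear) of 150.

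| n | Expected affected at 13% | Events for median | Probability at 13% | Events for finite lower limit (log-log) | Probability at 13% |
|---|---|---|---|---|---|
| 150 | 19.5 | 75 | 1e-27 | 63 | 1e-18 |
| 75 | 9.75 | 38 | 5e-15 | 29 | 2e-8 |
| 50 | 6.5 | 25 | 3e-10 | 18 | 3e-5 |
| 25 | 3.25 | 13 | 3e-6 | 8 | 1.1% |

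Per category, the Grade 3-5 rate can be no higher than the overall rate.

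**Last-contact censoring (SAP 7.6.2).** This needs assumptions that the documents do not give. With n = 150, crude incidence 13%, mean treatment of 4, 8 or 12 months capped at 24, and a constant or early-decaying hazard, the median and its lower limit were reached in 0 of 1,000 simulated trials in all six scenarios. The curve ended on average between 0.85 and 0.87. A second simulation (median treatment 6 months, median survival 12 or 24 months) reached the median in 0 of 1,500 trials at 13% and 0 of 1,500 at 25%. For n = 25 at 13% it was reached in at most 0.2%.

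**Own-window censoring (the parenthesis in 7.6.8.2 read as each subject's last dose + 100 days).** Same six scenarios, n = 150:

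| Hazard | Mean treatment | Median reached | Finite lower limit |
|---|---|---|---|
| Constant | 4 months | 16.7% | 52.9% |
| Constant | 8 months | 2.4% | 46.4% |
| Constant | 12 months | 0% | 8.5% |
| Early | 4 months | 0.1% | 2.7% |
| Early | 8 months | 0% | 0.1% |
| Early | 12 months | 0% | 0% |

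Separate runs under this reading gave 1-4% for the median at n = 150 and 6-10% at n = 25. When the median is reached here, it comes from late drops in the curve with few subjects still at risk.

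**The case against.** The strongest reply is that SAP 7.6.8.2 already plans an onset median among affected subjects, in the sentence before the Kaplan-Meier one, and that the Kaplan-Meier median is only an addition. This stands in part. A reader might infer that the trial will report nothing on onset, and the documents do not support that. However, the affected-subject summary is planned only by category, has no interval, and is not the method that SAP 7.6.2 and the synopsis give for the endpoint.

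Second, the Appendix 1 plot is already a cumulative-rate display. Under group-maximum censoring, subjects who die event-free stay in the denominator, so one minus the curve is a crude cumulative incidence. That is fair, but the text provides a plot, with no tabulated estimate and no interval at any time.

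Third, these are labelled descriptive statistics. That is right. No test or success rule depends on them, and the primary incidence analysis is untouched.

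Fourth, a reader might infer that the median can never be reached under any censoring rule. The own-window results above show otherwise, so the wording must be almost certainly not reached under the two rules as worded, and unlikely under the third reading.

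Fifth, the 13% covers Grade 3-5 only. Nothing can be concluded about the any-grade summaries in 7.6.8.2.

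**Conclusion.** The point holds for Grade 3-5 IMAEs. Under last-contact censoring (7.6.2) or group-maximum censoring (7.6.8.2), the all-treated Kaplan-Meier median will almost certainly be not reached, overall and in each group. Its confidence limits will be missing too, apart from about a 1% chance of a finite lower limit in a group of 25 under group-maximum censoring. Under the own-window reading the median was reached in 0 to 17% of simulated trials of 150.

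The group-maximum result rests only on the 13% rate and the group sizes, and holds far above that rate. The other two rest on assumed treatment durations, hazards and follow-up.

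The consequence is limited but real. An onset median will be reported by category, but the estimate that was meant to carry uncertainty will be blank. SAP 4.2 and 7.6.2 also leave unclear which of the two planned medians is the endpoint, and the censoring rules in 7.6.2 and 7.6.8.2 conflict.

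**What to change.** In SAP 7.6.2, the Grade 3-5 part of SAP 7.6.8.2, and the protocol synopsis:

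- **(a)** Name the median (range) among affected subjects, for any category together and by category, as the reported median time to onset.
- **(b)** Replace the all-treated Kaplan-Meier median for Grade 3-5 with the cumulative incidence of first Grade 3-5 IMAE and its 95% CI at fixed times, for example 3, 6, 12 and 24 months. Treat death without an IMAE as a competing event and end the at-risk period at last dose + 100 days.
- **(c)** Reconcile the censoring rules in 7.6.2, 7.6.8.2 and Appendix 1. State what happens to an event-free subject when the window closes, because the answer changes the curve. In the constant-hazard simulation with 4-month mean treatment, it ended on average at 0.64 with own-window censoring and 0.87 with group-maximum censoring.

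The any-grade Kaplan-Meier summaries may stay, since no any-grade rate is stated.

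The cost is minor rewording and one extra table, with a standard procedure and no new data. SAP 7.5.1.1 already plans fixed-time rates with intervals for overall survival, so the style of reporting is familiar within this plan.

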Patient-Reported Outcome Measurements	X			Prior to any study-related procedures: FKSI-19, and EQ-5D
Health Resource Utilization	X			Prior to any study-related procedures

Table 5.1-3: Follow-up Procedural Outline (CA209374)			
Procedure	Follow-up Visit 1 (X01) and Visit 2 (X02).	Follow-up after Visit 2 (X02)	Notes
			Follow up Visit (X01) = 30 days from last dose +/-5 days, or may be on date of discontinuation +/-5 days if the date of discontinuation is more than 35 days after last dose. Follow up Visit 2 (X02) = 100-114 days from last dose.
Vital Signs	X		
Physical measurements	X		Includes performance status (Karnofsky)
Adverse Events Assessment	X	X*	*Beyond 100-114 days from the last dose of study therapy, subjects will be followed for ongoing drug-related AEs until resolved, return to baseline or deemed irreversible, or until lost to follow-up or withdrawal of study consent.
Laboratory Tests	X		CBC with differential, serum chemistry (BUN or serum urea level, serum creatinine, albumin, sodium, potassium, calcium, magnesium, phosphate, chloride, bicarbonate, glucose), liver function (AST, ALT, total bilirubin, alkaline phosphatase, LDH), thyroid function (TSH, reflex to free T3 and free T4 if abnormal result)
Review of concomitant medications	X		
Pregnancy testing	X		Serum or urine
Collection of Survival Information	X	X	Every 3 months until death, lost to follow-up, or withdrawal of study consent for 5 years following start of therapy. May be performed by phone contact or office visit.
Radiographic Tumor Assessment	X	X	For subjects who discontinue study treatment for reasons other than PD, follow up scans (or MRIs when appropriate) should be performed every 8 weeks ( $\pm$ 5 days) for the first 13 months then every 12 weeks $\pm$ 1 week until PD, death, lost to follow-up, or withdrawal of consent. Radiographic assessments should not be delayed until the X01 or X02.

Table 5.1-3: Follow-up Procedural Outline (CA209374)			
Procedure	Follow-up Visit 1 (X01) and Visit 2 (X02).	Follow-up after Visit 2 (X02)	Notes
Patient Reported Outcomes			
FKSI-19 and EQ-5D	X	X	At X01 and X02 and then every 3 months for the first 12 months, then every 6 months thereafter, as permitted by local IRB. Assessments can be conducted by phone or mail.
Healthcare Resource Utilization	X	X	To be collected in alignment with PRO's above (, FKSI-19 and EQ-5D). Assessments can be conducted by phone or mail.

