### **7.6.8 Immune Mediated Adverse Events**

IMAEs are specific events occurring within 100 days of the last dose of study drug (which includes pneumonitis, diarrhea/colitis, hepatitis, nephritis/renal dysfunction, rash, and endocrine abnormalities [adrenal insufficiency, hypothyroidism/thyroiditis, hyperthyroidism, diabetes mellitus, and hypophysitis]), regardless of causality, for which subjects received immunosuppressive medication for treatment of the event. The exception to the immunosuppressive medication criteria for IMAEs is endocrine events (hypothyroidism/thyroiditis, hyperthyroidism, hypophysitis, diabetes mellitus, adrenal insufficiency), which are included regardless of treatment since these events are often managed without immunosuppression.

Unless otherwise specified, analyses will be performed by IMAE category on events where immune modulating medication was initiated. Analyses may also be repeated by categories of endocrine events.

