## **APPENDIX 1      ADVERSE EVENTS OF INTEREST DEFINITION AND CONVENTIONS**

The adverse events of interest including IMAE, select AE, and other event of special interest consist of a list of preferred terms grouped by specific category and by subcategory. These categories and subcategories are defined by the Sponsor and the list that is most current at the time of analysis will be used. Also changes may be made to this list with each new version of MedDRA.

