### **Time-to onset definition**

Time-to onset of AE (any grade) for a specific category (e.g. pulmonary events, gastrointestinal events, ...) is defined as the time between the day of the first dose of study treatment and the onset date of the earliest AE (of any grade) in this category.

If the subject did not experience an AE (of any grade) in the category, time-to onset will be censored at the maximum follow-up time of all subjects in their respective treatment group (i.e for subjects without an event, follow-up time is defined from first dosing date up to last dosing date +30 days (or 100 days depending on the analysis) if subjects are off treatment and followed for at least 30 days (or 100 days depending on the analysis) , otherwise it is defined up to the last known alive date). The resulting Kaplan-Meier plot will represent the cumulative rate of the select AE (any grade) in the category over time.

Time-to onset of AE (grade 3-5) for a specific category is defined similarly but restricted to grade 3-5 AEs.

Time-to onset of drug-related (grade 3-5 or any grade) AE for a specific category is defined similarly but restricted to drug-related AEs.

Time-to onset for a specific subcategory is defined similarly but restricted to event of this subcategory.

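### Two sets of SAP rules cover time to resolution and time to onset of high-grade IMAEs; under one of them a fatal event can count as resolved

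*SAP*

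**What the plan says.** SAP 4.2 names as secondary endpoints the median time to onset and median time to resolution of high-grade IMAEs, and a summary of subjects whose events resolve after immune-modulating or hormonal treatment begins. Two parts of the SAP then define these times.

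**SAP 7.6.2 (same wording in the protocol synopsis, Analyses).** For onset: "If a subject never experienced the given AE, the subject will be censored at the last contact date". For resolution: "Time to resolution is calculated from the AE onset date to AE end date", with censoring at last contact only if the event is still ongoing. There is no rule for fatal events or for several events in one subject, and no reference to Appendix 1.

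**SAP 7.6.8.2, 7.6.8.3 and Appendix 1.** For a subject without an event, "time-to onset will be censored at the maximum follow-up time of all subjects in their respective treatment group". An i.e. parenthesis follows: "follow-up time is defined from first dosing date up to last dosing date +100 days if subjects are off treatment" and have been followed that long, otherwise up to the last known alive date. Appendix 1 gives the purpose: "The resulting Kaplan-Meier plot will represent the cumulative rate of the select AE (any grade) in the category over time". For resolution, Appendix 1 takes the longest clustered event in a category and accepts a return to baseline grade. It treats an event as unresolved if it became Grade 5 or if its resolution date is the date of death, and censors it at the last known alive date. Appendix 1 covers IMAEs by name: "The adverse events of interest including IMAE, select AE, and other event of special interest consist of a list of preferred terms".

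The grade range also differs. The protocol (8.3.2 and the synopsis endpoint list) gives Grade 3-4 for these medians; SAP 4.2 gives Grade 3-4 and Grade 5.

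**The concern.** A programmer cannot follow both sets of rules for one endpoint, and nothing in the available text says which governs or that one is a sensitivity analysis. Protocol 8.4.3 (Secondary Analyses) appears in the table of contents, but its text is not in the public document.

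Resolution matters most. The secondary objective is the outcome of all high-grade IMAEs, expressly including Grade 5. Followed literally, SAP 7.6.2 can code a death as a resolution. That shortens the reported median, raises the share resolved, and makes outcomes look better than they were. In an open-label, single-arm study, leaving the choice open also allows it to be made after the data have been seen.

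Onset is a consistency point. SAP 7.6.8 restricts the event: "IMAEs are specific events occurring within 100 days of the last dose of study drug". Survival contacts run much longer: "Every 3 months until death, lost to follow-up, or withdrawal of study consent for 5 years following start of therapy". If last contact includes those contacts, SAP 7.6.2 keeps subjects in the risk set after they can no longer have a countable event, and also censors at death. The resulting curve is no longer the cumulative rate that Appendix 1 wants.

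**Working it through.** **Inputs from the documents.** N = 150 and an assumed Grade 3-5 IMAE rate of 13% (protocol 8.1); at most 24 months of treatment (protocol 3.1); a 100-day window after last dose (SAP 7.6.8); survival contact to 5 years (protocol Table 5.1-3).

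**The plan's own figure.** The plan states no figure for onset or resolution. The power figure that supplies N and the rate reproduces: P(X ≤ 20 | n = 150, p = 0.13) = 0.607, stated as 61%. The Clopper-Pearson interval for 20/150 is 8.34% to 19.84%, as in Table 8.1-1. Expected high-grade cases: 0.13 × 150 = 19.5, about 20.

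**Resolution: the same record under each rule**

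| Record | SAP 7.6.2 | Appendix 1 |
|---|---|---|
| Fatal IMAE, end date = date of death | Resolved on that date | Unresolved, censored |
| Fatal IMAE, left ongoing at death | Censored | Unresolved, censored |
| Return to baseline grade, no end date | Ongoing, censored | Resolved |
| Appendix 1's example: 1-5, 6-11 and 10-12 January | 5, 6 and 3 days, no rule for choosing | One cluster of 12 days |

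**Resolution: a hand check.** Assume 20 durations in days: 5, 8, 10, 12, 14, 17, 20, 24, 28, 32, 37, 43, 50, 58, 68, 80, 95, 115, 140, 180.
- All coded resolved (7.6.2): S = 10/20 = 0.50 at day 32, so the median is 32.
- Day-10 event fatal and censored (Appendix 1): S = 18/20 = 0.90 before it, then 17 at risk. S = 0.90 × 10/17 = 0.529 at day 32 and 0.90 × 9/17 = 0.476 at day 37. The median is 37, so the 7.6.2 value is (37 − 32)/37 = 13.5% shorter.
- Day-10 and day-17 events both fatal: the median is 43, so the 7.6.2 value is (43 − 32)/43 = 25.6% shorter.
- Share resolved: 20/20 against 19/20, or 5 points per fatal event.

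**Resolution: simulation.** There were 3,000 sets of 20 subjects in each of 18 combinations: median resolution 2-8 weeks, median onset to death 2-8 weeks, 10-30% of the others unresolved. One fatal event coded as resolved shortens the median by 3-17%; two shorten it by 6-30%. Only the fatal-event rule was varied.

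**Onset: how the rules differ.** Take ten subjects at times 1 to 10, with events at 2, 5 and 8.
- Censored at own time: S = 8/9 × 5/6 × 2/3 = 0.494.
- Censored at the group maximum: S = 9/10 × 8/9 × 7/8 = 0.700, which is 1 minus the crude 3/10.

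The maximum rule therefore returns the crude proportion.

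**Onset: simulation.** There were 2,000 trials of 150 per scenario, calibrated to 13% over complete windows. Assumed: survival median 25 months; treatment median 3.7, 5.5 or 9 months; last contact includes survival contacts. The last-contact Kaplan-Meier cumulative rate at the final analysis was:

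| Onset hazard | 3.7 mo | 5.5 mo | 9 mo |
|---|---|---|---|
| Constant | 15.0% | 15.6% | 16.4% |
| Halving every 6 months | 14.3% | 14.6% | 14.9% |
| Halving every 3 months | 14.0% | 14.1% | 14.2% |
| Halving every 1.5 months | 13.7% | 13.7% | 13.7% |

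Over survival medians of 15-35 months the range is 13.5-18.6%. The curve reached 50% in no simulated trial, so the all-treated median is not reached under this rule. Under the maximum rule the curve ends at about 13%, so the median is not reached there either.

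**The i.e. parenthesis.** Read as censoring each subject at the end of the subject's own window, it becomes a third rule. With a constant hazard and crude rates of 13.0-13.6%, that reading gave end-of-curve rates of 28-40%.

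**The case against.** The strongest reply is that Appendix 1 completes SAP 7.6.2 rather than contradicting it. It covers IMAEs by name, SAP 7.6.8.2 and 7.6.8.3 send the reader there, and the SAP history says version 2.0 modified the IMAE section, added Appendix 1 and added analysis detail. A programmer might reasonably apply Appendix 1 throughout. But SAP 7.6.2 does not cite it and gives its own, different rules, so this reading is possible rather than stated. The same history is equally consistent with SAP 7.6.2 not having been updated.

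Other points on that side stand:
- SAP 7.6.2 never says that death is a resolution. The conflict arises only if a fatal event is given an end date equal to the date of death; if it is left ongoing, both rules censor. Appendix 1 provides for such end dates, so the case was foreseen, but its frequency is unknown.
- Appendix 1 works by category, so pooling 20 cases is an illustration and not an analysis it specifies. Clustering and return to baseline grade were not quantified, and 3-17% is not the net difference between the two sets of rules.
- Last contact date is not defined in the available text. The onset figures assume that it includes survival contacts.
- The Grade 3-4 wording in the protocol endpoint lists is a minor lapse: the protocol objectives and the synopsis analysis text include Grade 5.

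**Conclusion.** The conflict is real on the text and should be corrected before the analysis. Its weight lies in resolution: one fatal IMAE coded as resolved shortens the pooled median by about 3-17% and raises the share resolved by 5 points, given about 20 high-grade cases, the assumed timings, and an end date recorded as the date of death.

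Onset is secondary. Last-contact censoring gives about 14-16% against 13% over most of the central assumptions, and only in the Kaplan-Meier cumulative rate.

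Some stronger inferences are not supported:
- That the primary result is affected. Incidence is a simple percentage of treated subjects and uses neither rule.
- That the onset median is biased. Median, minimum and maximum among subjects with events do not depend on censoring, and the all-treated median is not expected to be reached under either written rule.
- That group-maximum censoring is itself wrong. Once every window has closed (24 + 100/30.4375 = 27.3 months after the last first dose), it gives the crude proportion, as intended. It understates the eventual rate only at earlier cuts, and the SAP's Schedule of Analyses does not say that onset is reported at those.

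That the documents set no precedence is a statement about the available text; protocol 8.4.3 could not be checked.

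**What to change.** 1. In SAP 7.6.2, replace the last-contact onset rule and the AE-end-date resolution rule with a reference to Appendix 1. State there that a fatal event, or a resolution date equal to the date of death, is unresolved and censored at the last known alive date.
2. State that, for any analysis pooled across categories, all high-grade IMAEs form one category under the Appendix 1 rules. Without this, step 1 would leave a pooled analysis undefined.
3. Apply the same resolution definition to the resolution summary in SAP 4.2.
4. Reword the i.e. parenthesis in SAP 7.6.8.2 and Appendix 1 so that it plainly defines the follow-up over which the group maximum is taken.
5. Align the protocol synopsis analysis wording with the SAP, and the Grade 3-4 range in the protocol endpoint lists with Grade 3-4 and Grade 5 in SAP 4.2.
6. If onset curves are shown at a cut before all 100-day windows have closed, add a note that the group-maximum rule understates the eventual cumulative rate. No further method is needed.

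The cost is a few wording changes in the SAP and protocol, with no new data and no change to sample size or power. Reported time to resolution may look slightly longer.
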